# **EFFECT OF 6-WEEKS CONTENT KNOWLEDGE WORKSHOP ON WRITTEN TEST PERFORMANCE AMONG PHYSICAL EDUCATION STUDENT IN CHINA**

## **Executive Summary**

[figure not shown]
The employment survey of Chinese students found that it is very difficult for students majoring in physical education to find jobs. The analysis found that the main factor causing employment difficulties is that Chinese students have very low written test achievements. However, content knowledge determines the student's written test achievement. Therefore, to solve student employment difficulties, the student's written test achievement and improving the students' written test achievement through experimental design and quantitative research methods.

This experiment aims to use two different teaching methods to intervene in students' learning and find out which teaching method is more conducive to improving students' written test achievement. The experiment will use a 6-week workshop intervention to enhance students' written test achievement. The experiment is divided into workshop groups and standard teaching groups. The most significant difference between the two groups is that the workshop group has oral links and guarantees. The similarities between the two groups are: The same teacher qualifications; The same intervention time; The same content; The same research objects.

Based on content knowledge learning, content knowledge is divided into six categories for detailed intervention. We will do a 6-week intervention for two groups (workshop style and standard teaching style). After that, we will assess their progress based on writing tests that the Examination agency develops.

The difference between the two is whether there is a video teaching link, and the same is that there are oral links. The entire experiment was carried out in the classroom with the school's consent. Use written exams to check student scores. Students have special teachers responsible for teaching specific content knowledge during class, standard learning after class does not require special care, and the experiment is not risky.

# 1. Research Framework

This experiment aims to provide a theoretical basis for improving teaching methods. Increase the employment rate of students and ease the employment pressure of students.

The research framework mainly includes three parts: experimental group, control group, and workshop. Through 6 weeks of workshop and six weeks of standard teaching, the content knowledge was intervened. Interventions include: 1) Sports training design. Teaching design. 2) Muscle function system. 3) Exercise physiology system. 4) Competition venue planning. 5) Referee rules. Workshop groups and standard teaching groups both use test paper types to analyze data. After the intervention, the differences between the workshop and the standard groups were compared through paper analysis. The written test includes pre-test and post-test.

Based on a systematic literature review. It can support my research. To do this, we will progressively analyze the theoretical framework. Based on the Schulman study, CK is divided into CCK and SCK. First and foremost, CCK includes basic physical education knowledge, health promotion knowledge, and physical exercise knowledge. Then, continue to be divided into one part: Sports training. Design, Teaching design, Muscular, functional system, Exercise physiological system, Competition venue planning, Referee rules. According to Mao's literature, these six parts of sports content knowledge are what students need to learn.

On the other hand, Specialized Content Knowledge -skills, the -Skill test is Motor skills Knowledge. Including Technical ability, Physical ability, Technical and tactical.

Last one teacher recruitment, you see, when you want to recruitment teacher in China, 70% is based on written test, you see interview only 30%, which in

including skill, so how also to be for you get a job, you need to score in the written test. According to the finding from the research, in China, all the students did very poorly in the written test. China is not doing very well, but the study showed that they have workshops for teachers to improve their skills. But they have never done for the student. That is why we want to try workshop apply the workshop to the student. Based on the literature review, whether we can see the same achievement as the teacher, I think the workshop may help, but only you know after your data. It is better on the but, we don't know workshop on students, that is why we want to the students, I think workshop, compared to the workshop on students follow on workshop on the teacher, as student follow the standard teaching as, the school better on the written test.

## **2.Explain in detail the research design that we have employed in this study**

### **a)The research design outline**

A good research design should have these characteristics: eliminating deviation, avoiding confusion, controlling irrelevant variables, and testing the statistical accuracy of the hypothesis (Wellesma et al., 2010) . In addition, we must follow the basic theoretical knowledge of research and design. Therefore, the following is discussed in detail based on the research outline.

a) To establish a cause and effect relationship between the workshop and students ' written test performance.

The simplest experimental design

- i) Randomly select subjects from College students majoring in physical education.
- ii) Workshop group - receives treatment.
- iii) standard teaching - does not receive treatment.

b) When to use experimental procedures?

- i) Between the workshop and students have written test performance.
- ii) Control for all variables that might influence the outcome.
- c) Used when comparing workshop, and standard teaching group
  - i) Random assignment - assign individuals to random groups.
  - ii) Control over extraneous variables that might influence the relationship - influence in participant selection, procedures, statistics, or the design likely to affect the outcome.
  - iii) Manipulation of the treatment conditions - manipulate the workshop to determine the effect on the outcome.
  - iv) Outcome measures - assess whether the treatment conditions influence an outcome (Students' written test performance
  - vi) Group comparisons - compare students' written-test performance for different treatment.
- f) Guard against threats to validity - guard against false conclusions.

## **b) Design details**

### **Part Two**

[figure not shown]
This research design refers to the plan or strategy of conducting a six-week content knowledge intervention on students' written test achievements. The experiment design refers to the plan of six specific contents and knowledge that we planned to improve students' written test achievements. The experiment design can be constructed by determining, setting, and establishing variables of students' written test achievements in the experiment. Include independent variable content knowledge, including experimental variables and other variables that exist reliably.

- 1) The first part studies the design process. Next, the research design uses a quantitative research design.

The research design uses a quantitative research design. According to the specific design of the experiment, we intervene with the experimental and choose true experimentally. according to this type of experiment, we adopt type 1 true experimental. It includes the pre-test post-test control group. It combines the samples and periods of the 6-week test on the influence of content knowledge on students' written test achievement and is based on the pre-test post-test control group standard teaching. We focus on students' content knowledge test before the test (before the first week) and after the test (after the sixth week). In the six-week content knowledge intervention, the researcher conducts an experimental and control groups experiment. Individuals in the experimental group receive the experimental treatment, whereas those in the control group do not.

Table 1. Effect of 6-weeks content knowledge workshop on written test performance-  
-research designs

Pre- and Posttest Design		Time →		
Random assignment	standard teaching Group	Pretest Before the first week,	No Treatment	Posttest After the sixth week
Random assignment	Workshop Group	Pretest Before the first week,	Experimental Treatment	Posttest After the sixth week

The second part is an introduction to research and design.

i) Definition of this experiment.

On the one hand, according to the nature of educational evaluation measurement, the experiment belongs to achievement tests because achievement tests are used to examine students' mastery of specific learning experiences that have occurred and to measure students' learning effects (Kellogg, 1997).

Six weeks' content knowledge is the measurement content. In addition, the test content classification description is based on achievement tests. Achievement tests are divided into comprehensive achievement tests and single-subject achievement tests. Based on the 6-week content knowledge classification, the test belongs to the complete achievement test. Finally, the achievement test is compiled and analyzed. The establishment of achievement tests includes standard teachingized achievement tests and teacher's self-made achievement tests.

This research design is a standard teachingized test because this research achievement test was evaluated by six experts in the field of content knowledge. Six experts, including three American experts and three Chinese content knowledge experts, demonstrated. Three American experts are doctoral supervisors at Ohio State University, and they are essential researchers and discoverers of content knowledge.

ii) Choice is an true experiment.

The experimental control in actual experimental design strictly obeys the three basic principles of repetition, randomization, and local control. In addition, actual experiments comprise the most rigorous and robust experimental methods because of equating the groups through random assignment. In actual experiments, we randomly assign students to workshop groups and standard teaching groups. Individuals in the workshop group receive the experimental treatment, whereas those in the standard teaching group do not. After we administer the treatment, we compile average (or mean) scores on a posttest. One variation on this design is to

obtain pretest as well as posttest measures or observations. When we collect pretest scores, we will compare net scores (the differences between the pre-and post-test).

At the same time, in the design of the influence of 6 weeks' content knowledge on students' written test achievements, we must: a) Randomly select and allocate subjects. b) Accurately manipulate independent variables. c) Strictly control the effect of extra variables or evenly disperse interference variables.

Table 5. Two-way Breakdown of 6-weeks Content Knowledge Design

Content		CAQs	MAQs	T/F AQs	SAQs	EAQs	Knowledge	Understanding	Application	Analysis	Synthesis	Judgment	Score
Sports Training Design	Classify				√	√	-	-	5	5	5	-	15
	Application					√							
Basketball Class Hour Teaching Plan	Objectives				√	√	5	5	-	5	5	-	20
	Contents												
	Steps				√	√							
Energy Supply System	Three						5	-	-	5	5	-	15
	Systems					√							
	Source		√										
Exercise prescription	Conceptual	√					-	-	5	5	5	-	15
	Elements		√	√	√								

Bloom divided the teaching objectives of cognitive activities into six sides: knowledge, understanding, application, analysis, synthesis, and judgment. The first two parts are the learning and understanding of knowledge; the last four parts are applying knowledge. Use six different levels to exam content knowledge

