Moreover, the validity. Based on the analysis of content validity. In our study, we defined this method as usually a logical analysis. That is to say, not only it focuses on the six-week content knowledge validity analysis, but it also relies on experts to analyze all the questions in the written test and classifies all the questions bidirectionally according to the content distribution and examination objectives of the written test, thus completing the "two-way breakdown of 6-weeks content knowledge examination". Then, based on the analysis of "Two-way breakdown of 6-weeks content knowledge examination", experts commented and judged the satisfaction of the content validity of written test measurement. "Two-way breakdown of 6-weeks content knowledge examination" reliable and valid analysis. According to the validity and reliability requirement, we completed its design(Yan, 2011). In this process, we should pay attention to the following problems: compare the consistency between the content of the highlighted test and the content knowledge, and divide the proportion according to the content knowledge of 6 weeks. Determine whether the test content fully covers the scope of the conceived content. Examination questions must be consistent with measurement objectives. Students' achievements in 6 weeks' content knowledge will be tested by written tests, requiring objective grading and scoring standard teachings.

In the last place, comprehensive factors. Ensure that the sources of reliability and validity are similar to those of college students majoring in physical education. Master the characteristics of standard

teaching and workshop groups be before the test. The empirical reliability data and validity data were collected before the experiment to prove that the test experiment we chose is suitable for college students majoring in physical education. The reliability coefficient comes from the Journal of educational psychology.

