## 12.Data Analysis

Table 12. Data Analysis - Base on Hypothesis

Research Objective	Research Hypothesis	Data Analysis
1.Basic theoretical knowledge	1.1 There is significant difference between the control group and the experimental group in the Sports training design written test performance among P E students in China.	Two-way ANOVA
	1.2 There is significant difference between the control group and the experimental group in the Teaching design written test performance among	Two-way ANOVA

	P E students in China.	
2.Health promotion knowledge	2.1 There is significant difference between the control group and the experimental group in the Muscle function system written test performance among PE students in China.	Two-way ANOVA
	2.2 There is significant difference between the control group and the experimental group in the Exercise physiology system written test performance among PE students in China.	Two-way ANOVA
3.Physical exercise knowledge	3.1 There is significant difference between the control group and the experimental group in the Competition venue planning written test performance Among PE students in China.	Two-way ANOVA
	3.2 There is significant difference between the control group and the experimental group in the Referee rules written test performance among PE students in China.	Two-way ANOVA

Based on the research objective, focus on the research hypothesis. To achieve the research hypothesis, we must use t-way ANOVA analyses.

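### Table 5 as shown allots no points to venue planning, referee rules or the Judgment level, although six topics and six levels are to be tested

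*Protocol*

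**What the plan says.** Table 5 (Protocol, section 2 b, Part Two) is titled "Two-way Breakdown of 6-weeks Content Knowledge Design". It assigns item types, points by cognitive level and a score to each topic. Four topics are scored: "Sports Training Design" 15, "Basketball Class Hour Teaching Plan" 20, "Energy Supply System" 15 and exercise prescription 15. The Judgment column holds a dash in every row. No grand total is given. The paragraph below names the six Bloom levels, Judgment being the sixth, and ends "Use six different levels to exam content knowledge".

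Other sections work with six topics:

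- Section 3, Tables 6 and 8: six topics, one per week. Track and field venue planning is week 5 and basketball rules week 6.
- Section 10 a, item iii: the content falls into six categories and the comprehensive test covers them.
- Section 12, Table 12: one hypothesis per topic. Hypothesis 3.1 reads "There is significant difference between the control group and the experimental group in the Competition venue planning written test performance" and 3.2 makes the same claim "in the Referee rules written test performance among PE students in China". These two are the whole of the third objective, physical exercise knowledge.
- Section 9, item v: experts classify all questions of the written test by content and objective, which completes the two-way breakdown, and judge content validity from it. One of the listed checks is "Determine whether the test content fully covers the scope of the conceived content".

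**The concern.** The written test is the trial's only outcome, and each hypothesis in Table 12 concerns one topic's score. A topic without points in the blueprint has no planned subscore. If the paper follows Table 5 as it appears, the third objective yields no data at pretest or posttest, and no analysis can repair that once the pretest has been given.

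The gap also touches the validity evidence. Section 9 rests content validity on expert judgement of the two-way breakdown. A breakdown that leaves out a third of the taught content would fail the coverage check that the protocol sets itself.

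**Working it through.** **Inputs.** The level points and scores come from Table 5, the teaching schedule from Tables 6 and 8, and the hypotheses from Table 12.

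**Step 1: reproduce the row scores in Table 5.**

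| Topic | Knowledge | Understanding | Application | Analysis | Synthesis | Judgment | Sum | Stated |
|---|---|---|---|---|---|---|---|---|
| Sports training design | – | – | 5 | 5 | 5 | – | 15 | 15 |
| Class hour teaching plan | 5 | 5 | – | 5 | 5 | – | 20 | 20 |
| Energy supply | 5 | – | – | 5 | 5 | – | 15 | 15 |
| Exercise prescription | – | – | 5 | 5 | 5 | – | 15 | 15 |
| Column sum | 10 | 5 | 10 | 20 | 20 | 0 | 65 | not given |

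All four rows reproduce, and the columns add to the same total: 10 + 5 + 10 + 20 + 20 + 0 = 65. The listed rows are therefore internally intact. This says nothing about rows that are not listed.

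**Step 2: compare topics taught, tested and scored.**

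| Week | Topic | Hypothesis | Points in Table 5 |
|---|---|---|---|
| 1 | Sports training design | 1.1 | 15 |
| 2 | Teaching design | 1.2 | 20 |
| 3 | Muscle function / energy supply | 2.1 | 15 |
| 4 | Exercise physiology / exercise prescription | 2.2 | 15 |
| 5 | Venue planning | 3.1 | none shown |
| 6 | Referee / basketball rules | 3.2 | none shown |

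**Step 3: size.**

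- Topics and hypotheses without points: 2 of 6.
- Teaching time on them in the workshop arm: 2 weeks × 1 session × 3 h = 6 h of 18 h.
- Teaching time on them in the standard arm: 2 weeks × 2 sessions × 1.5 h = 6 h of 18 h.
- Levels without points: 1 of 6.

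**Step 4: would two missing rows be plausible?** The protocol states no total for the paper. If it were marked out of 100 (an assumption), 100 − 65 = 35 points would be unallocated. If out of 120 (also an assumption), 120 − 65 = 55. Listed rows carry 15 or 20 points, so two more of that size would add 30 to 40 and bring the total to between 95 and 105. A 100-mark paper with two further rows would fit, but the document does not say so.

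**The case against.** A reader might infer that hypotheses 3.1 and 3.2 have no items to test them. The document does not support that. Table 5 is a blueprint, and section 6 lists the two-way table and the written test paper as separate instruments. The paper itself is not shown. The executive summary says that an examination agency develops the tests, and section 10 says that all six categories are tested. Nothing states that the paper leaves out the two topics. What stands against this is section 9, by which the breakdown classifies every question. On that description, a topic absent from the breakdown has no classified question. Section 9 uses a slightly different name for the table, but Table 5 is the only one of its kind in the protocol.

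The stronger objection is that the two rows may have been lost when the file was read. The unscored topics are exactly the last two in teaching order, the table has no total row to check against, it is visibly disordered in places, and the table numbering jumps from 1 to 5 nearby. On the other side, the explanatory text runs straight on after the fourth row with no sign of a missing figure, and Tables 8 and 10, which are also split in the copy read, kept their content. Neither side settles it. A loss cannot be excluded.

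The Judgment point is weaker still. The six-level sentence introduces a framework and does not say that each level must carry points, and any Judgment points could sit in the same two rows. It is secondary and shares the same doubt.

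**Conclusion.** The contradiction holds for the table as shown: four topics and five levels carry points, against six topics taught, six categories said to be tested, six hypotheses and six levels named. If the paper is built to this table, hypotheses 3.1 and 3.2 cannot be tested and the third objective goes unscored.

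This rests on two assumptions: that Table 5 in the sponsor's original has only these four rows, and that the paper follows it. Neither can be confirmed from the protocol, so confidence is low. The point still deserves action, because checking is trivial and an omission could not be mended after the pretest. If the original contains the two rows, the main point falls away. The Judgment point then remains only if those rows also leave that level empty.

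**What to change.** Before the pretest:

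1. Confirm against the original that Table 5 is complete.
2. If the rows for track and field venue planning and basketball rules are absent, add them with item types and points, so that each of the six hypotheses in Table 12 has its own subscore.
3. State the paper's total score.
4. Have the six experts re-check content validity on the completed table.
5. Secondary: give Judgment points in at least one row, or state that five levels are examined.

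If the rows already exist, the cost is one look at the source file. If not, it is some test construction and one further pass by experts who are already involved. No extra students are needed.

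Suggested wording, if the rows have to be added: *The written test allots points to each of the six topics in Table 8, as set out in Table 5; the topic subscores are the outcomes for hypotheses 1.1 to 3.2, and their sum is the stated total of the paper.*

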### 3. Intervention Plan

Table 6. Intervention Plan Design

Group	Experiment Group -Workshop			Control Group - standard teaching teaching		
Week	1-2	3-4	5-6	1-2	3-4	5-6
Content Knowledge Category 	Sports Training Design And Teaching Design	Muscular Functional System And Exercise Physiological System	Competition Venue Planning And Referee Rules	Sports Training Design And Teaching Design	Muscular Functional System And Exercise Physiological System	Competition Venue Planning And Referee Rules
	i) Basketball Weekly Training Plan ii) Basketball Class Hour Teaching Plan	i) Energy Supply System ii) Exercise Prescription	i) Track And Field Venue Planning ii) Basketball Rules	i) Basketball Weekly Training Plan ii) Basketball Class Hour Teaching Plan	i) Energy Supply System ii) Exercise Prescription	i) Track And Field Venue Planning ii) Basketball Rules
Workshop	Workshop Criterion 1			Workshop Criterion 1		
standard teaching	Consistent Criterion					
Duration Time	3 Hours / Total Hours 18			1.5 Hours / Total Hours 18		
Frequency	1 Time / Week			2 Times / Week		
Number Of Week	6 Weeks			6 Weeks		

 Article 27 of the "Interim Regulations on Public Recruitment of Public Institutions". Written test subject category. Primary and secondary school teachers (Class D).

General intervention plan design is an overall overview of the experiment. The whole experiment is divided into two interventions (workshop group and standard teaching group), mainly analyzed from two aspects (same and different). Detailed analysis, one is that the two groups have the same 6-week intervention, the total time is the same, and the intervention content is the same. The second is that it doesn't work. Workshop once a week, once every 3 hours. standard teaching group twice a week, once for 1.5 hours.

Table 7. Intervention Plan-Same Characteristics

Content	Workshop Group and standard Teaching Group
Teacher qualification	Same qualification and titles
	Both have one teacher
	Same teaching experience and research area
Student qualifications	Same age , PE students No students have received this courses prior to the study

The analysis of intervention Plan-same characteristics mainly includes two parts: Teacher qualification and student qualifications. In the first part, workshop group and standard teaching group, teacher Qualification, same qualification and titles, both have one same teacher majors: physical education, similar experience: minimum more than ten years.No students have received this courses before the study. The second part is the age, major and educational background of students. Students with similar educational backgrounds, aged between 19 and 25, are all majors in physical education.No students have received these courses before the study.

Table 8. Six-weeks Workshop and standard teaching Intervention Details

Week	Content 		Workshop group		Week	standard teaching group
1	Basic theoretical knowledge	Sports training design	Weekly basketball training plan	3H/1time/week	1	Weekly training plan  1.5H / 1 time / week.
						Weekly training plan 1.5H / 1 time / week
2		Teaching design	Class hour basketball teaching plan	3H/1time/week	2	Class hour teaching plan  1.5H / 1 time / week.
						Class hour teaching plan 1.5H / 1 time / week.
3	Health promotion knowledge	Muscular functional system	Energy supply system	3H/1time/week	3	Energy supply system  1.5H / 1 time / week.
						Muscle exercise 1.5H / 1 time / week.
Week	Content 		Workshop group		Week	standard teaching group

 Xia Jinyang. Thinking about the proposition width of sports theory test questions [J]. Sports Culture Guide, 2010,{4}(08):79-82+90.

 Tian maijiu. 《Sports Training》. Beijing: Higher Education Press, July 2006. Chapter 12. Weekly Training Plan and Organization Plan. p369-397.

 Mao Zhenming. School Physical Education, 3rd Edition. Beijing: Higher Education Press, July, 2017. Chapter 8. Physical Education Teaching Design and Plan. Class Hours Teaching Plan (Teaching Plan) 131-142.

 Deng Shuxun. Exercise Physiology. Beijing: Higher Education Press, July 2005. Chapter 1: Energy supply of muscle activity. Three systems of energy supply of muscle activity. P11-20.

 Article 27 of the "Interim Regulations on Public Recruitment of Public Institutions". Written test subject category. Primary and secondary school teachers (Class D).

4		Exercise physiological system	Exercise prescription	3H/1time/week	4	Exercise prescription  1.5H / 1 time / week.
						Exercise prescription 1.5H / 1 time / week.
5	Physical exercise knowledge	Competition Venue planning	Track and field venue planning	3H/1time/week	5	Track and field venue planning 1.5H / 1 time / week.
						Track and field venue planning  1.5H/1time/week.
6		Referee rules	Basketball rules	3H/1time/week	6	Basketball rules  1.5H / 1 time / week.
						Basketball rules 1.5H / 1 time / week.

This part discusses the details of the 6-weeks workshop and standard teaching intervention. First and foremost, CK includes three categories. The deeper level is divided into six parts; the specific content has methods and plans, Basketball weekly training plan, Basketball class hour teaching plan, Energy supply system, Exercise prescription, Track and field venue planning, Basketball rules. On the other hand, there are two lessons; each class is 1.5 hours.

7 Deng Shuxun. Exercise Physiology. Beijing: Higher Education Press, July 2005. Chapter 3 Physical Fitness and Exercise Prescription. P229-235.

8 Li Hongjiang. Track and Field, Beijing: Higher Education Press, June 2014. Chapter 6 Basic knowledge of track and field. Design and layout of track and field. P104-111.

9 Wang Jiahong. Basketball, Beijing: Higher Education Press, December, 2015. Chapter 17 Referees in Basketball Match. Main Referees in Basketball Match. P291-299.

This is a one-class training plan, mainly divided into other structures. A training session explicitly includes three parts.

To start with, the intervention content Specifically including step 1-An overview, and introduction, step 2-Students formed groups, step 3-Oral test assessment. The first part includes: The teacher introduced the purpose of the study, expectations, and discussion of the principles of sports training design. They were learning content related to design and muscle function and exercise physiology system—rest time.

The second part includes, The teacher introduced the purpose of the study, expectations, and discussion of the principles of sports training design. They were learning content related to design and muscle function and exercise physiology systems. Rest time Divided into three groups and rotated roles of teacher, students, 8 / group. They were learning by the reciprocal peer learning instructional model.

The third part includes the teacher introduced the purpose of the study, expectations, and discussion of the principles of sports training design. They were learning content related to design and muscle function and exercise physiology systems. Rest time Divided into three groups and rotated roles of teacher, students, 8 / group. They were learning by the reciprocal peer learning instructional model. Students were prompted to switch teacher roles, student every 10 min—evaluation through check sheets and oral test ( 90% or better correct answers ).

On the other hand, time allocation, including specific time allocation.

Table 9. Workshop Methods-Class Hours Teaching Plan

Content	Workshop -Intervention (I) - 3 Hour/1 times / Week		Time-Minute
One lesson Training plan	Part 1 An overview and introduction	a) The teacher introduced the purpose of the study, expectations. b) Discussion of the principles of sports training methods and plans. c) Show the content knowledge in the situation with charts.	4
		3	
		3	
		a) Learning design. b) Muscle function. c) Knowledge of sports physiological system content .	10
	10		
	10		
	Rest time.	10	
	Part 2 Grouping teaching	a) Have group discussions with students. b) Divided into three groups and rotated roles of teacher, students, eight people in each group. c) They are learning by the reciprocal peer learning instructional model.	10
			20
			10
	Part 3 Oral examination assessment	a) Teachers use questions to guide students to think and discuss. b) Students were prompted to switch roles of teacher, student every 10 min. c) Teaching explanation and demonstration. d) Students discuss and reflect.	10
			10
			10
The oral test requires that the correct rate of answers is greater than 90%. a) Encourage students and give good behavioral performance. b) True and false questions performance. c) Essay questions performance.		20	
		20	
20			

Table 10. Workshop Methods-Class Hours Teaching Plan

Content	Workshop -Intervention (II) - 3 Hour/1 times / Week		Time-Minute
Track Meet Rules	Part 1 An overview and introduction.	a) The teacher introduced the purpose of the study, expectations. b) Discussion of the principles of sports training methods and plans. c) Show the content knowledge in the situation with charts.	4
			3
			3
	Part 2 Watching the workshop video clips.	Students are asked to watch instructional videos.	20
		a) Teachers focus on teaching specific steps. b) Common mistakes. c) Correcting mistakes.	10
			5
			5
		Students are asked to explain or demonstrate teaching tasks.	20
		Rest time.	10
	Part 3 Oral examination assessment.	a) Have group discussions with students. b) Divided into three groups and rotated roles of teacher, students, Eight people in each group. c) They are learning by the reciprocal peer learning instructional model.	10
			10
			10
		Students were prompted to switch roles of teacher, student every 10 min.	10
		The oral test requires that the correct rate of answers is greater than 90%.	20
		a) Encourage students and give good behavioral performance. b) True and false questions performance. c) Essay questions performance.	
		20	
	20		

Three hours workshop intervenes in specific content and specific time. Take a workshop as an example to analyze; the others are only different in scope, time, and intervention steps are the same. The workshop consists of 3 stages. To begin, the intervention content. The first stage includes an overview and introduction; The second stage comprises watching the workshop video clips; The third stage comprises oral test assessment. In addition, this essay will discuss time allocation.

Table 11. standard teaching -Class Hours Teaching Plan

Content	Total 1½ Hour / 2 Times / week			Time Minute
One Lesson Training plan	Part 1 Beginning part	Teaching objectives	Skill objective.	5
			Participation objective.	5
			Health objective.	5
			Social adaptation objective.	5
		Contextual import	Improve students' interest in teaching objectives.	5
	Part 2 Basic part	Students	Answer the questions.	5
			Perception of the teaching material.	5
			Active learning.	5
			Understanding of the teaching material.	10
			Consolidate the knowledge.	10
		Teachers	Rest time.	10
			The leader of the teaching.	5
			Explain the content.	5
			The teaching method.	5
	Part 3 End part	Teacher and student	Summary.	3
			Homework.	2

Based on the three-hour standard teaching intervention, the specific content of the intervention, and the particular time statistics. Take standard teaching as an example to analyze; the others are only different in scope, time, and intervention steps are the same.

This part discusses the details of the 6-weeks workshop and standard teaching intervention. First and foremost, CK includes three categories. Then, the deeper level is divided into six parts: methods and plans, class hour teaching plan, muscle exercise, energy supply, breathing and exercise circulation and exercise, athletic and basketball venue, basketball, and football rules. On the other hand, there are two lessons; each class is 1.5 hours.

